4.3 STATISTICAL SIGNIFICANCE LEVELS

As this is a pilot trial, no inferential between-group comparisons will be undertaken (i.e. there will be no between-group hypothesis testing). Feasibility outcomes, such as recruitment rates, will be presented with two-sided 95% confidence intervals. Between-group differences for proposed trial outcomes will be summarised descriptively and presented with two-sided 75%, 85% and 95% confidence intervals, as recommended by Lee et al (2014)²³.

Estimates that may be used for future sample size calculations (e.g. standard deviation of proposed primary outcome, correlation between baseline and follow-up measure) will be presented with two-sided 80% and 90% confidence intervals (Browne (1995)).

4.4 INTERIM ANALYSIS

There is no planned interim analysis for this pilot trial. If, for any reason, the Trial Steering Committee (TSC) requests an interim analysis of the data, efforts will be made to appoint a statistician independent of the trial team to undertake such work, in order to retain the blinding of the trial statistician.

4.5 TIME POINTS OF STATISTICAL ANALYSIS

Statistical analysis will be undertaken once the final group of participants has completed the final assessment at 180 (± 14) days post-randomisation and the database is locked.

4.6 DERIVED VARIABLES

The following variables will require coding to calculate scores for analysis:

- *MELD Score* – Specifications of how to calculate the MELD score are in detailed in **Error! Reference source not found.** N.B. the maximum MELD score is 40
- *Child Pugh Score* – This score consists of five items each with a score of 1 to 3. The Child Pugh score is the total of all five items, giving a total score of between 5 and 15 points. Further details of how each item is scored is detailed in **Error! Reference source not found.**
- *SADQ Score* – The score is the sum of all 20 items of the SADQ and can be between 0 and 80. A score of:
 - <16 usually indicates only a mild physical dependency
 - 16 – 30 indicates moderate dependence
 - >30 indicates severe alcohol dependence¹⁹
- *WEMWBS* – The score is sum of all the items from the questionnaire and can be any value from 14 to 70²⁰
- *SWEMWBS* – The raw score (sum of all 7 items of the SWEMBS) needs to be converted to the metric score using the conversion table from Stewart-Brown, et al.²¹ in **Error! Reference source not found.** (Table 21).

4.7 MISSING DATA

One of the objectives of this pilot trial is to assess the completeness of potential outcome measures for the definitive trial, at the level of both item and outcome measure. Missing outcome data will be noted and used to inform the likely pattern of missing data in a full-scale trial. If a considerable amount of outcome data is missing, this may suggest a need to reconsider the choice of outcome measures and in particular inform the choice of primary outcome measure for any future definitive trial. This may also provide an insight into how missing data can be minimised in any subsequent full-scale trial.

4.7.1 Imputation

Imputation will only be performed for missing questionnaire items when a small proportion of items are missing from an individual response. Where possible, validated, published guidelines will be followed. Any participant who misses a follow-up visit or the whole outcome measure/questionnaire, will not be imputed for that time-point or measurement. Any missing clinical measures, such as the Child Pugh score and MELD score, will not be imputed.

The published guidelines for imputation of the proposed outcomes are summarised below:

- *WEMWBS* – Impute missing items if no more than 3 are missing. The guidance suggests using the mean of all responses for the missing item or the mean of the non-missing items for the participant as possible imputation methods²⁴.

- SWEMWBS – The transformations set out in Table 17 are only valid when the response is complete, i.e. no missing values, therefore no imputation will be performed for this measure²⁴.

5 STATISTICAL ANALYSES

As the study is a pilot trial, it is not suitably powered to be able to support or justify any conclusions regarding treatment efficacy/effectiveness realised from hypothesis testing, and indeed that is not the purpose of the study. As such, the analysis of the results of this trial will not involve formal, inferential statistical comparisons or hypothesis testing between groups. Analyses will be descriptive with the view to informing the design of a fully powered MIRAGE randomised controlled trial.

Continuous measures will be summarised as means, standard deviations and ranges where the distribution appears approximately normally distributed, and as medians, inter-quartile ranges and ranges otherwise. Categorical data will be summarised by frequencies and percentages. Where appropriate, parameter estimates (e.g. between-group differences) will be presented with confidence intervals.

Analysis of quantitative data will be conducted to summarise pilot outcomes, evaluate acceptability of and concordance with the FIT intervention, and the completion and summary statistics of the planned primary and secondary patient-reported and clinical outcomes measures. In addition, appropriate plots will be used to illustrate key data and assess potential between-group differences.

5.1 STUDY POPULATION

Data from the screening process through to the completion of the trial will be recorded and presented in a CONSORT-style flow diagram (see Figure 2). In particular, the following data will be provided:

- Number of people invited to participate
- Number of people screened for eligibility
- Number (percentage) of people ineligible
- Number (percentage) of people eligible and asked to participate
- Number (percentage) of people who declined to participate
- Number (percentage) of people consented to participate
- Number (percentage) of participants who consented to participate but did not proceed to randomisation
- Number (percentage) of participants randomised to each allocated group
- Number (percentage) of participants who did not receive their allocated treatment
- Number (percentage) of participants who did receive their allocated treatment
- Number (percentage) of participants who completed the 28 (± 7) days post baseline assessment
- Number (percentage) of participants who completed the 90 (± 7) days post baseline assessment
- Number (percentage) of participants who completed the 180 (± 14) days post baseline assessment
- Number (percentage) of participants lost to follow up
- Number (percentage) of participants analysed

5.1.1 Baseline Characteristics and Demographics

Baseline characteristics, collected prior to randomisation, will be summarised by allocated group to informally check for balance between groups and provide an overview of the study sample (see **Error! Reference source not found.**). No inferential analysis baseline data by of allocated groups will be undertaken²², but any considerable imbalance will be noted to inform the design of the full trial.

5.1.2 Participants who Discontinue, Withdraw or are Lost to Follow-up

It is possible that participants will withdraw consent part way through the trial, or their treatment may be discontinued due to medical reasons. It is unlikely in this trial that a participant will be discontinued on medical grounds (for either allocated group), but for reasons such as injury, some participants may not be able to complete the trial. Participants who discontinue will be categorised as follows:

- Continue to consent for follow-up and data collection
- Consent to use pre-collected data only
- Complete withdrawal of consent to use any data

Reasons for withdrawal or loss to follow up will be summarised where reported, at each stage of the process (**Error! Reference source not found.**), including withdrawal prior to randomisation, participants who did not receive their allocated treatment, non-completion of treatment, lost to follow-up.

Participants who withdraw from the study, or whose treatment is discontinued on medical grounds, will not be replaced although their available data will be used unless they have specifically requested for it to be removed from the database. The extent of discontinuation, withdrawal and loss to follow up will be used to inform the design of the fully powered subsequent study, predominantly to ensure a sufficiently powered trial after allowing for losses to follow-up.

5.2 ANALYSIS OF PILOT OUTCOME MEASURES

In addition to the summary statistics detailed in section 5.1, the following data will be summarised:

- Time to recruit total study sample
- Number (percentage) of participants who completed TAU before recruitment or after recruitment but before baseline assessment, and number (percentage) of participants who completed TAU post-baseline assessment, in total and by site
- Time elapsed, by allocated group, of:
 - baseline assessment to randomisation
 - baseline to 28 (± 7) day assessment
 - baseline to 90 (± 7) day assessment
 - baseline to 180 (± 14) day assessment
- Number of assessments completed within the 28, 90 and 180-day assessment windows
- Acceptability of and adherence of FIT programme:
 - Number (percentage) of participants in the intervention group who completed:
 - all FIT sessions
 - ≥ 2 FIT sessions
 - FIT session 1 along with at least one of FIT session 2 or FIT session 3
 - each of the nine FIT sessions
- Number (percentage) of participants re-hospitalised

- Number (percentage) of participants who relapsed to alcohol use.
- Time elapsed between randomisation and start of the FIT sessions
- Number (percentage) of FIT sessions delivered within the specified time frame (see Figure 1 for specified time frames)
- Number (percentage) of participants who attended at least four FIT sessions before the 28 day assessment
- Number (percentage) of participants who attended at least seven FIT sessions before the 90 day assessment
- Number (percentage) of participants who attended at least nine FIT sessions before the 180 day assessment
- Time elapsed between the last FIT session participant attended and the 180 day assessment
- Number who attended final fit session after 180 day assessment
- Feasibility of using the proposed patient- and clinician-reported outcome measures. For each outcome measure we will report (by allocated group and overall):
 - Number (percentage) of participants who completed all items of the outcome measure (if relevant)
 - Number (percentage) of participants with a valid total score for each outcome measure, allowing for appropriate imputation methods if available.

5.3 PRELIMINARY ASSESSMENT OF FIT

As this is not a fully powered trial, it is inappropriate to perform any formal hypothesis tests comparing the allocated groups. However, to provide a preliminary assessment of whether FIT is a potentially useful treatment for patients with ArLD, we will calculate summary statistics for each of the participant-reported and clinical outcomes listed in section 0, by allocated group.

For continuous outcomes, we will produce boxplots and calculate the mean and corresponding confidence interval by allocated group for the measure at 28, 90 and 180 days and the change between baseline and 28, 90 and 180 days.

The simple, unadjusted estimated between-group difference of the change between baseline and 28, 90 and 180 days for each continuous outcome will be presented with the corresponding confidence intervals. The between-group differences, and corresponding 95% confidence intervals, adjusted for stratification variables will also be calculated using multivariable linear regression. The model will include both of the stratification variables (dichotomised baseline SADQ score and site).

For binary outcomes, we will produce calculations of the frequency and percentage (with corresponding exact 95% confidence interval) by allocated group. The unadjusted and adjusted between-group differences will be reported, derived from logistic regression models, with dichotomised baseline SADQ score and site included in the adjusted model.

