15. COLLECTION, STORAGE AND ANALYSIS OF CLINICAL SAMPLES

It is the responsibility of the trial site to ensure that samples are appropriately labelled in accordance with the trial procedures to comply with the 2018 Data Protection Act. Biological samples collected from participants as part of this trial will be transported, stored, accessed and processed in accordance with national legislation relating to the use and storage of human tissue for research purposes and such activities shall at least meet the requirements as set out in the 2004 Human Tissue Act and the 2006 Human Tissue (Scotland) Act.

The following clinical samples will be obtained:

• A urine sample for direct alcohol metabolites - at Day 180

Detailed instructions on the collection, recording and processing of samples will be provided to sites in a separate manual, provided by PenCTU.

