- *Time to relapse* – Self-reported time to relapse to regular alcohol use, defined as ≥ 5 drinking days per week, or ≥ 5 units in a single day
- *Alcohol metabolites* – a urinary sample will be used to measure ethyl glucuronide ($\mu\text{g/L}$) and ethyl sulphate ($\mu\text{g/L}$), which provide a highly sensitive and specific objective quantitative measure of alcohol consumption within the preceding 72 hours
- *EuroQol 5 Dimension 5 Level (EQ-5D-5L)*¹⁶ – This quality of life questionnaire, commonly used in health economics, consists of five questions, where each question/item can be scored between 1 (no problems) and 5 (extreme problems). Further information is provided in the HEAP
- *Resource Use Questionnaire (RUQ)* – see the separate HEAP for details.

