Fibrosis			
Cirrhosis			
Child-Pugh Score			
Mean (SD) [range]			
Median (IQR)			
MELD Score			
Mean (SD) [range]			
Median (IQR)			

*Participants can provide data in more than one category – percentages will not necessarily add to 100%

Table 10: Summary statistics for the proposed primary and secondary outcome measures by allocated group

Variable	Time point	TAU			FIT + TAU		
		N	Mean (SD) (95% CI)/Median [IQR]	Range	N	Mean (SD) (95% CI) /Median [IQR]	Range
Alcohol Use (grams of pure alcohol/ week)	baseline						
	28 (±7) days						
	90 (±7) days						
	180 (±14) days						
SADQ Score	baseline						
	28 (±7) days						
	90 (±7) days						
	180 (±14) days						
WEMWBS	baseline						
	28 (±7) days						
	90 (±7) days						
	180 (±14) days						
SWEMWBS	baseline						
	28 (±7) days						
	90 (±7) days						
	180 (±14) days						
Ethyl Glucuronide (µg/L)	180 (±14) days						
Ethyl Sulphate (µg/L)	180 (±14) days						
Re- hospitalisation*	180 (±14) days						

* Rates and corresponding confidence intervals given for re-hospitalisation

Table 11: Summary statistics for the changes between baseline and 28, 90, and 180 day assessments for proposed primary and secondary outcomes including only those participants who complete all follow-up visits

Variable	Time point	TAU			FIT + TAU		
		N	Mean (SD) Change From Baseline (95% CI)/Median [IQR]	Range	N	Mean (SD) Change From Baseline (95% CI) /Median [IQR]	Range
Alcohol Use (grams of pure alcohol/ week)	28 (±7) days						
	90 (±7) days						
	180 (±14) days						
SADQ Score	28 (±7) days						
	90 (±7) days						
	180 (±14) days						
WEMWBS	28 (±7) days						
	90 (±7) days						
	180 (±14) days						
SWEMWBS	28 (±7) days						
	90 (±7) days						
	180 (±14) days						

Table 11b: Proportion of participants who completed TLFB assessment and with no alcohol consumption as calculated from TLFB

Variable	Time point	TAU	FIT + TAU
		N (% of participants with complete TLFB)	N (% of participants with complete TLFB)
Participants with zero alcohol consumption	Baseline		
	28 (±7) days		
	90 (±7) days		
	180 (±14) days		

Table 12: Re-hospitalisations by allocated group

Re-hospitalisation	TAU N (%)				FIT + TAU N (%)			
	0	1	2	>2	0	1	2	>2
No. of re-admissions								
By 28 (± 7) days								
By 90 (± 7) days								
By 180 (± 14) days								

Table 13: Proportion of participants who relapse and time to relapse to alcohol use by allocated group

	TAU	FIT + TAU
N (%) who relapsed by:		
28 (± 7) days		

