90 (± 7) days		
180 (± 14) days		
Time to relapse (days)	Median (Inter-quartile Range) [Range]	Median (Inter-quartile Range) [Range]

Table 14: Unadjusted between-group differences and confidence intervals for proposed primary and secondary outcome measures, with unadjusted confidence intervals

Variable	Time Point	Mean Between-group Difference	Unadjusted 95% CI	Unadjusted 85% CI	Unadjusted 75% CI
Alcohol Use (grams of pure alcohol/ week)	28 (± 7) days				
	90 (± 7) days				
	180 (± 14) days				
SADQ Score	28 (± 7) days				
	90 (± 7) days				
	180 (± 14) days				
WEMWBS	28 (± 7) days				
	90 (± 7) days				
	180 (± 14) days				
SWEMWBS	28 (± 7) days				
	90 (± 7) days				
	180 (± 14) days				
Ethyl Glucuronide ($\mu\text{g/L}$)	180 (± 14) days				
Ethyl Sulphate ($\mu\text{g/L}$)	180 (± 14) days				
Re-hospitalisation*	180 (± 14) days				

* Rates and corresponding confidence intervals given for re-hospitalisation

Table 15: Between-group differences and confidence intervals for proposed primary and secondary outcome measures, adjusted for stratification variables (dichotomised baseline SADQ score and site)

Variable	Time Point	Adjusted Mean Between-group Difference	Adjusted 95% CI	Adjusted 85% CI	Adjusted 75% CI
Alcohol Use (grams of pure alcohol/ week)	28 (± 7) days				
	90 (± 7) days				
	180 (± 14) days				
SADQ Score	28 (± 7) days				
	90 (± 7) days				
	180 (± 14) days				
WEMWBS	28 (± 7) days				
	90 (± 7) days				
	180 (± 14) days				
SWEMWBS	28 (± 7) days				
	90 (± 7) days				
	180 (± 14) days				
Ethyl Glucuronide ($\mu\text{g/L}$)	180 (± 14) days				
Ethyl Sulphate ($\mu\text{g/L}$)	180 (± 14) days				
Re-hospitalisation*	180 (± 14) days				

* Rates and corresponding confidence intervals given for re-hospitalisation

Table 16: Unadjusted between-group differences and confidence intervals of change from baseline for proposed primary and secondary outcomes

Variable	Time Point	Mean Between-group Difference of Change From Baseline	Unadjusted 95% CI	Unadjusted 85% CI	Unadjusted 75% CI
Alcohol Use(grams of pure alcohol/ week)	28 (± 7) days				
	90 (± 7) days				
	180 (± 14) days				
SADQ Score	28 (± 7) days				
	90 (± 7) days				
	180 (± 14) days				
WEMWBS	28 (± 7) days				
	90 (± 7) days				
	180 (± 14) days				
SWEMWBS	28 (± 7) days				
	90 (± 7) days				
	180 (± 14) days				
Ethyl Glucuronide ($\mu\text{g/L}$)	180 (± 14) days				
Ethyl Sulphate ($\mu\text{g/L}$)	180 (± 14) days				

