Table 17: Between-group differences and confidence intervals for of change from baseline for proposed primary and secondary outcome measures, adjusted for stratification variables (dichotomised baseline SADQ score and site)

Variable	Time Point	Adjusted Mean Between-group Difference of Change From Baseline	Adjusted 95% CI	Adjusted 85% CI	Adjusted 75% CI
Alcohol Use (grams of pure alcohol/ week)	28 (± 7) days				
	90 (± 7) days				
	180 (± 14) days				
SADQ Score	28 (± 7) days				
	90 (± 7) days				
	180 (± 14) days				
WEMWBS	28 (± 7) days				
	90 (± 7) days				
	180 (± 14) days				
SWEMWBS	28 (± 7) days				
	90 (± 7) days				
	180 (± 14) days				
Ethyl Glucuronide ($\mu\text{g/L}$)	180 (± 14) days				
Ethyl Sulphate ($\mu\text{g/L}$)	180 (± 14) days				

Table 18: Estimates of standard deviations of proposed primary outcome (alcohol use) for informing sample size calculations for a definitive trial

Parameter	Point Estimate	80% CI*	90% CI*
Standard deviation of alcohol use at baseline			
Standard deviation of alcohol use at 180 (± 14) days assessment			
Standard deviation of change in alcohol use between baseline and 180 (± 14) days assessment			

* upper bound of two-sided confidence interval relevant as conservative estimate for sample size calculations

Table 19: Estimates of correlation coefficients for proposed primary outcome (alcohol use) for informing sample size calculations for a definitive trial

Parameter	Point Estimate	80% CI*	90% CI*
Correlation coefficient between baseline and 180 (± 14) days assessment of alcohol use			
Correlation coefficient between baseline and change between baseline and 180 (± 14) days assessment of alcohol use			

* lower bound of two-sided confidence interval relevant as conservative estimate for sample size calculations

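### Urine EtG and EtS are sampled only at day 180, yet a change from baseline is planned, and no analysis estimates the proportion positive by arm

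*SAP*

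**What the plan says.** **Sampling.** Protocol section 15 lists one specimen: "A urine sample for direct alcohol metabolites - at Day 180". Protocol 4.4.1, 10.4 and Table 1 agree, and SAP Table 1 marks alcohol metabolites at 180 days only.

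**What the marker measures.** In SAP 3.4.3, "a urinary sample will be used to measure ethyl glucuronide" and ethyl sulphate in µg/L, which are said to "provide a highly sensitive and specific objective quantitative measure of alcohol consumption within the preceding 72 hours". The protocol files the marker under exploratory outcomes (4.4.1). The SAP lists it among proposed secondary outcomes for the definitive trial.

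**By-arm summary.** SAP 5.3: "For continuous outcomes, we will produce boxplots and calculate the mean and corresponding confidence interval by allocated group". SAP section 5 gives means for roughly normal data "and as medians, inter-quartile ranges and ranges otherwise", and the Appendix A summary table that includes EtG and EtS allows either form.

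**Between-group estimates.** SAP 5.3 applies the difference in change from baseline to each continuous outcome, without exception. In Appendix A, Tables 14 and 15 give EtG and EtS a mean difference in level, unadjusted and adjusted. Tables 16 and 17 list them again, under "Mean Between-group Difference of Change From Baseline" and "Adjusted Mean Between-group Difference of Change From Baseline".

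**What is absent.** No positivity cut-off, no rule for results below the assay limit, and no number or percentage positive. SAP 5.3 does have a method for binary outcomes, and self-reported abstinence over 7 days is reported as a proportion (3.4.3, Table 11b).

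**The concern.** There are two separate defects.

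The first is a plain inconsistency. A change from baseline needs a baseline value, and none is collected. The EtG and EtS rows of Tables 16 and 17 therefore cannot be completed, and the sentence in 5.3 that generates them should not cover these outcomes.

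The second is the choice of contrast. A marker with a 72-hour window, described by its sensitivity and specificity, most naturally answers a yes/no question: had this person drunk in the last three days? The plan does not estimate that by arm. Its only derivable contrast is a difference in mean concentration, which a few very high values can dominate if the distribution is skewed.

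What is at stake is the objective cross-check on self-report. Alcohol use, SADQ and relapse all come from participants who know their allocation, although the assessors are blinded. As the SAP puts the marker forward for the definitive trial, the pilot is also the place to try out how it should be analysed.

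**Working it through.** **1. The plan's own figures.** With 90 randomised 1:1 and 75% retention (SAP 3.5), each group has 45 × 0.75 = 33.75, stated as a minimum of 33. The retention interval at its widest is 1.96 × √(0.5 × 0.5 / 90) = 10.3 points (exact method 10.7), within the stated ±11%. Both reproduce. The documents give no SD, effect size or cut-off for EtG or EtS, so nothing specific to the marker can be reproduced.

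**2. Change from baseline.** Change = day-180 value − baseline value. The second term does not exist for any participant, so the rows are underivable. No assumption is needed.

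**3. Assumptions for the contrast (not in the documents).** Value zero without recent drinking; log-normal with log-SD s from 1.0 to 2.5 otherwise; 33 per arm; positive 50% TAU v 30% FIT, or 67% v 47%. The 67% borrows the two-thirds six-month relapse figure in protocol section 1. That figure is for alcoholic hepatitis and is not a 72-hour rate. The 20-point gap is illustrative.

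**4. Why the mean is weak under that shape.** With median m among positives, the expected difference in means is (p₁ − p₂)·m·e^(s²/2). Its ratio to its standard error is

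(p₁ − p₂) / √{[(p₁ + p₂)·e^(s²) − p₁² − p₂²] / n},

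so m cancels, and s = 0 gives the ratio for the difference in proportions. For 67% v 47% and n = 33:

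- proportions (s = 0): 0.20 / √[(1.14 − 0.6698)/33] = 0.20 / 0.1194 = 1.68
- mean, s = 1: 0.20 / √[(1.14 × 2.718 − 0.6698)/33] = 0.20 / 0.271 = 0.74
- mean, s = 2: 0.20 / √[(1.14 × 54.60 − 0.6698)/33] = 0.20 / 1.366 = 0.15

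**5. Simulation.** At least 20,000 trials per scenario; unequal-variance standard error with t quantile for the mean difference, Wald interval for the proportions. Exclusion of zero is counted in FIT's favour. Where two figures appear, repeat runs differed by a point.

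| Positive, TAU v FIT | log-SD | Mean difference null or wrong-signed | Its 95% CI excludes 0 |
|---|---|---|---|
| 50% v 30% | 1.0 | 17–18% | 16–17% |
| | 1.5 | 25–26% | 9% |
| | 2.0 | 30% | 5% |
| | 2.5 | 32–33% | 3% |
| 67% v 47% | 1.0 | 21% | 13–14% |
| | 1.5 | 29–30% | 7–8% |
| | 2.0 | 34% | 4% |
| | 2.5 | 36–37% | 3% |

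In every row the difference in proportion positive is null or wrong-signed in about 6% of trials (strictly wrong-signed in about 4%), and its 95% CI excludes zero in about 41%.

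At the planned 75% level (67% v 47%; log-SD 1.0, 1.5, 2.0), the mean difference excludes zero in 40%, 33% and 28% of trials, against 71% for the proportions. If only 25 per arm give a sample, the 95% figures are 11%, 6% and 4%, against 33%.

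**6. Precision of the alternative.** 95% half-width at 67% v 47%: 1.96 × √[(0.67 × 0.33 + 0.47 × 0.53)/33] = 23.4 points. At 50% v 30%: 23.1 points.

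**7. What the planned by-arm summary shows on the same data.** Reading the medians, with the upper quartile as tie-break, favours FIT in about 92% of trials, against about 94% for the proportion. The medians alone carry less: at 50% v 30% both are zero in about half of trials; at 67% v 47% in about 1%.

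**The case against.** The strongest reply is that the plan already shows most of what matters. Medians, quartiles, ranges and boxplots by arm are provided for, and under the same assumptions they point the right way nearly as often as the proportion does. This stands. A reader might infer that the marker is analysed only as a mean difference and cannot show whether fewer FIT patients are drinking. The documents do not support that: the mean is the sole planned basis for the between-group estimate, not for the by-arm description. What remains missing is an estimate of the difference in positivity with an interval.

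A reader might also infer that results below the assay limit would be treated as missing under SAP 4.2 and 4.7.1, so that abstainers drop out. That is speculative. A below-limit result is a result, and the documents do not say how the laboratory reports low values. The secure point is that no rule is given.

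Other points with force: the skewed shape and the 20-point effect are assumed; the protocol warns that alcohol biomarkers are inaccurate or untested in liver disease (4.4), while the simulation assumes perfect classification; the plan excludes hypothesis testing, so exclusion of zero is only a yardstick for information; promise is judged on self-reported grams (protocol 17.4); no progression criterion uses urine (SAP 5.5). A dichotomy also ignores amount, which the proposed primary outcome measures. These limit the importance of the point, and argue for adding the proportion rather than discarding concentrations.

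Finally, the table shells are labelled as examples, and empty rows bias nothing. But the instruction also stands in the text of 5.3, so it still needs correcting.

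**Conclusion.** The point holds in two parts. Without any assumption, the planned EtG and EtS change from baseline cannot be derived, and no planned analysis estimates the proportion positive by arm or its difference. Conditional on a spike near zero with a right-skewed tail, 33 samples per arm and a 20-point difference in positivity, the only derivable between-group estimate is much the poorer guide to direction: null or wrong-signed about three to six times as often as the difference in proportions (18% to 37% against 6%). The size of that gap depends on the assumed log-SD. The consequence is modest. The marker is exploratory in the protocol, by-arm summaries give partial information, and even the better contrast is accurate only to about ±23 points at 95%, so it would remain descriptive. It is worth correcting because it is cheap and this is the only objective alcohol measure.

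**What to change.** 1. Delete the EtG and EtS rows from Tables 16 and 17, and exempt these outcomes from the change analysis in SAP 5.3.
2. In SAP 3.4.3 and 5.3, classify each day-180 sample as positive or negative for EtG and for EtS at the analysing laboratory's reporting cut-off, with below-limit results counted as negative. The cut-off must come from the laboratory, as the documents give none. Report number and percentage positive by arm, among participants with an assayed sample, with exact confidence intervals. Give the unadjusted and adjusted between-group difference with the planned 75%, 85% and 95% intervals. State the scale: the logistic model in 5.3 yields odds ratios directly, so a difference in proportions has to be derived from its predictions.
3. Summarise concentrations as median, IQR and range. Any mean difference kept in Tables 14 and 15 should be supplementary, not the sole contrast.

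Cost: SAP text, table shells and a little more analysis; no new samples, visits or staff. The dichotomy ignores amount among positives, which the retained concentration summaries partly cover. SAP version 1.1 records changes made after database lock with statisticians unblinded, so if this is adopted at that stage it should be dated and labelled as a late addition.
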